6.4.2.5 Quality of Life (FACT-Hep)

The total score of the FACT-Hep QoL instrument will be calculated, the scores of each domain (Physical Well-Being, Social/Family Well-Being, Emotional Well-Being, Functional Well-Being), Hepatobilliary Cancer subscale (HCS), FACT-hep trial outcome index and each question at each time-point and their differences from baseline will be determined. The scoring algorithm is in Appendix 4.

The time to deterioration in QoL is defined as the time from date of randomization to the assessment date when the change from baseline in FACT-Hep Total Score is ≥7 points or date of death, whichever occurs first.

TTDQoL (Months) = (Date of change from baseline in FACT-Hep \geq 7 or death) – Date of Randomization +1.

The censoring is performed as follows:

- If a patient does not have a baseline FACT-Hep assessment, then the TTDQoL time will be censored at the randomization date, regardless of whether or not TTDQoL has been observed
- If a patient does not have a post-baseline FACT-Hep assessment, then the TTDQoL time will be censored at the date of randomization.

6.4.3 Additional Efficacy Variables

6.4.3.1 Child-Pugh Score Status

Severity of liver disease will be assessed according to the Child-Pugh classification of Severity of Liver Disease (see Appendix 5).

6.4.3.2 Depth of Response

Depth of Response (DpR) is defined as the maximum tumor shrinkage observed in a patient.

6.4.3.3 Early Tumor Shrinkage

Early tumor shrinkage (ETS) is defined as the percent of decrease of the sum of longest diameter of the target lesions at the first post baseline tumor assessment.

6.4.3.4 HCC Tumor Marker - AFP

AFP will be collected along with laboratory data and will be presented similarly. Change from baseline will be calculated.

AFP response, defined as a ≥50% decrease in AFP levels for patients with a baseline AFP level of ≥200 ng/mL, will also be calculated.

6.5 Safety Assessments

6.5.1 Extent of Exposure and Compliance to Study Treatment

6.5.1.1 Extent of Exposure to TheraSphere

A lobar dose is defined as TheraSphere dosing to a particular lobe, there may be more than 1 mass treated within the lobe.

Dose delivered to the lobe

The dose delivered to a particular lobe is equal to the weighted average of the dose delivered to each perfused liver tissue mass in that lobe. The target liver masses are used to weight the average.

Let M_1 and M_2 denote the total dose delivered to the first and second perfused liver masses respectively (where T_1 and T_2 are the first and second masses in kg), then the weighted average dose is computed as $[(T_1*M_1)+(T_2*M_2)]/(T_1+T_2)$

The data below show an example for one patient:

| Prior or Post Progression? | Lobe | Target liver mass, kg (T) | Total dose delivered to the perfused liver tissue, Gy (M) | Dose delivered to the lobe, Gy |
|-------------------------------|-------|------------------------------------|--|--------------------------------------|
| | Right | 1.3 | 115.2 | |
| Prior to progression | Right | 1.2 | 117.4 | 116.26 |
| Post-progression | Right | 1.3 | 108.2 | 108.2 |

For the patient above, the dose delivered to the right lobe prior to progression is calculated as:

$$\frac{(1.3 \times 115.2) + (1.2 \times 117.4)}{(1.3 + 1.2)} = 116.26 \text{ Gy}$$

Dose delivered to the lungs

The total dose delivered to the lungs is calculated as the cumulative sum of the dose delivered to the lungs from each treatment.

In addition:

Time to first angiogram will be calculated as:

Time to first angiogram (weeks) = (Date of first angiogram – Date of Randomization + 1)/7

Time to first TheraSphere treatment will be calculated as:

Time to first TheraSphere treatment (weeks) = (Treatment Date – Date of Randomization + 1)/7

Time between TheraSphere treatments will be calculated as:

Time between TheraSphere treatment (weeks) = (Treatment Date – Date of Previous Treatment + 1)/7

6.5.1.2 Extent of Exposure to Sorafenib

Sorafenib information will be presented by duration, cumulative dose and dose intensity.

Dose and duration of sorafenib includes:

- Cumulative dose (mg)
- Dose intensity (mg/month)
- Relative dose intensity (%)
- Duration of treatment (month)

Time to the first dose of sorafenib will be calculated as:

Time to first dose of sorafenib (weeks) = (first dose date – date of randomization + 1)/7

The cumulative dose of sorafenib (mg) will be the sum of all calculated administered doses per patient.

Duration of sorafenib in months will be calculated as:

Duration of treatment (months) = (date of last dose of sorafenib – date of first dose of sorafenib)/30.4375

Dose intensity of sorafenib (mg/month) per patient will be calculated as:

Dose intensity (months) = cumulative dose of sorafenib / duration of treatment (months)

Relative dose intensity of sorafenib (%) will be the dose intensity divided by the one month equivalent (2 * 400 mg * 30.4375 = 24,350 mg/month).

Relative dose intensity (%) = (monthly dose intensity / (24,350 mg/month) * 100

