# Treatment Arm Study Treatment (TheraSphere)

Within 2 weeks from randomization, hepatic angiography will be performed to assess hepatic vascular anatomy and tumor hypervascularity, followed by a 99mTc-MAA scan to rule-out gastrointestinal flow or unacceptable lung shunting. Embolization may be performed, if necessary, to close off gastrointestinal flow or to perform tumor redistribution so that the patient can meet eligibility criteria.

Patients will not be eligible for TheraSphere infusion if the potential radiation dose to the lungs exceeds 30 Gy for a single treatment or cumulative 50 Gy or embolization cannot be performed to effectively block GI blood flow from the hepatic arterial system. If radiation exposure to the lungs exceeds 30 Gy, dose reduction of TheraSphere is permitted (minimum dose allowed is 80 Gy ± 10%). These patients will be eligible to receive sorafenib SOC therapy and will be included in the Treatment Arm Intent-to-Treat analysis, but not in the Treatment Arm Per-Protocol analysis.

TheraSphere Treatment: TheraSphere treatment should occur within 28 days of randomization. The number of infusions required to achieve lobar treatment will be determined by the Investigator, based on the hepatic vascular anatomy.

Patients will receive TheraSphere, at a dose consistent with the approved product label, to the treated lobe of the liver. A target dose of 120 Gy ± 10% is advised. Thera Sphere Re-treatment: Re-treatment of the same patient/lobe with further cycles of TheraSphere is permitted if a treatable progression is detected during follow-up evaluations. Any retreatment should take place at least 28 days from the last TheraSphere treatment administered to that lobe. Patients can receive a subsequent TheraSphere administration in the absence of radiological progression criteria at investigator discretion. Patients must meet initial eligibility criteria to receive subsequent treatments. A maximum of three (3) TheraSphere administrations are permitted in total.

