#### 9.2.16.1.1 RE-TREATMENT

Patients can receive a subsequent TheraSphere administration in the absence of radiological progression criteria at investigator discretion. During follow-up, for patients in the Treatment arm who have demonstrated hepatic progression with hepatic lesions amenable to TheraSphere., re-treatment with TheraSphere is allowed. Any re-treatment should take place at least 28 days from the last TheraSphere treatment.

Patients must meet initial eligibility criteria for TheraSphere treatment (Section 8.1) to receive subsequent treatments. A maximum of three (3) TheraSphere administrations are permitted in total.

Patients will undergo additional pre-treatment evaluations as described in Section 9.2.16.1.2 at the investigator's discretion prior to administration of subsequent TheraSphere treatments to assess and address any changes in extra-hepatic shunting that may have developed.

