6.4.1 Primary Efficacy Variable – Overall Survival (OS)

The primary study endpoint is OS defined as the time from date of randomization until date of death due to any cause. For each patient that is not known to have died, OS will be censored at the time of last contact date known to be alive (contacts considered in the determination of last contact date include adverse event start and end dates, lesion assessment date, and best available care start and end dates).

Overall Survival (months)= (Date of event/censor – Date of Randomization + 1)/30.4375.

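### Sorafenib treatment duration leaves out one day, so dose intensity is overstated for short exposures and undefined when first and last dose share a date

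*SAP*

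**What the plan says.** SAP 6.5.1.2 builds sorafenib exposure from three definitions.

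- Numerator: "The cumulative dose of sorafenib (mg) will be the sum of all calculated administered doses per patient".
- Duration: "Duration of treatment (months) = (date of last dose of sorafenib – date of first dose of sorafenib)/30.4375".
- Dose intensity: "Dose intensity (months) = cumulative dose of sorafenib / duration of treatment (months").

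Relative dose intensity is the monthly dose intensity as a percentage of a one-month equivalent, given as "2 * 400 mg * 30.4375 = 24,350 mg/month". No rule covers a duration of zero. SAP 8.10.1.2 reports cumulative dose, dose intensity, relative dose intensity and duration with n, mean, standard deviation, median, minimum and maximum.

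Most other SAP durations count both end dates. Overall survival is an example: "Overall Survival (months)= (Date of event/censor – Date of Randomization + 1)/30.4375". Time to progression (6.4.2.1), both follow-up durations (6.5.1.3) and time to first sorafenib dose, in the same subsection 6.5.1.2, do the same. SAP 6.2.1 makes the date of first sorafenib dose relative day 1 for safety endpoints.

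For the other arm, SAP 6.5.1.1 gives "Time between TheraSphere treatment (weeks) = (Treatment Date – Date of Previous Treatment + 1)/7". Protocol 9.2.16.1.1 states the spacing as "Any re-treatment should take place at least 28 days from the last TheraSphere treatment". The protocol synopsis ties it to the lobe: "Any retreatment should take place at least 28 days from the last TheraSphere treatment administered to that lobe".

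**The concern.** The dose intensity ratio counts days differently above and below the line. A patient who takes sorafenib on relative days 1 to d has d days of dosing in the numerator but d − 1 days in the denominator. The benchmark is a per-calendar-day figure, so a patient who took every planned dose does not come out at 100%.

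Relative dose intensity is what a reader will use to judge how fully the active control was given. Protocol 5.3 notes that sorafenib dose reductions and drug holidays are often needed, so the question will be asked. The distortion is largest in patients who stop within days or a few weeks. Such patients can set the reported maximum and pull the mean. The trial ended early, and SAP 7.7 cites the limited number of patients, so each of them carries more weight. A patient with a single day of dosing produces a division by zero.

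**Working it through.** **Inputs.** All come from SAP 6.5.1.2 unless stated: planned dose 2 × 400 = 800 mg per day; month length 30.4375 days; duration = (last date − first date)/30.4375; cumulative dose = sum of administered doses. Let d be the number of calendar days from first to last dose, both included.

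**1. The plan's own figure.** 2 × 400 × 30.4375 = 24,350 mg/month, which matches the SAP exactly.

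**2. Relative dose intensity for a fully dosed patient.** Assume 800 mg on each of the d days, including both end days.

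- SAP formula: 800d ÷ [(d − 1)/30.4375] ÷ 24,350 = d/(d − 1).
- Inclusive formula: 800d ÷ [d/30.4375] ÷ 24,350 = 1, that is 100%.

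| d (days) | SAP duration (months) | Inclusive duration (months) | SAP formula | Inclusive formula |
|---|---|---|---|---|
| 1 | 0 | 0.033 | undefined | 100% |
| 2 | 0.033 | 0.066 | 200% | 100% |
| 7 | 0.197 | 0.230 | 116.7% | 100% |
| 14 | 0.427 | 0.460 | 107.7% | 100% |
| 28 | 0.887 | 0.920 | 103.7% | 100% |
| 84 | 2.727 | 2.760 | 101.2% | 100% |
| 180 | 5.881 | 5.914 | 100.6% | 100% |

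**3. Reduced doses.** The two formulas share a numerator, so their ratio is d/(d − 1) at any dose level. At half dose for 28 days the SAP formula gives 51.9% instead of 50.0%. At half dose for 7 days it gives 50 × 7/6 = 58.3%.

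**4. Effect on an arm mean.** The documents do not say how many patients will have short exposure, so this is an assumed illustration. Take 20 patients: 19 with a true value of 80% over 84 days, and one at full dose for a varying time. The true mean is (19 × 80 + 100)/20 = 81.0% throughout. Under the SAP formula the 19 each show 80 × 84/83 = 80.96%. The printed mean is then:

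- twentieth patient treated 84 days: (19 × 80.96 + 101.2)/20 = 82.0%
- 14 days: (19 × 80.96 + 107.7)/20 = 82.3%
- 7 days: (19 × 80.96 + 116.7)/20 = 82.7%
- 2 days: (19 × 80.96 + 200)/20 = 86.9%
- 1 day: no value, so the mean covers the other 19 only.

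**5. TheraSphere interval.** For a gap of g days the SAP prints (g + 1)/7 weeks, against g/7 by subtraction. The difference is 1/7 = 0.14 weeks.

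| Gap (days) | SAP (weeks) | Subtraction (weeks) |
|---|---|---|
| 26 | 3.86 | 3.71 |
| 27 | 4.00 | 3.86 |
| 28 | 4.14 | 4.00 |

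Only a gap of exactly 27 days moves from below 4 weeks to 4 weeks.

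**The case against.** The strongest objection concerns the numerator. The SAP speaks of calculated administered doses without giving the calculation, so the exact factor rests on counting a full dose on both end days. If a patient took half the daily dose on each end day, the cumulative dose would be 800(d − 1) mg and the SAP formula would give exactly 100%. This stands as a limit on the size. It does not rescue the formula. Protocol 9.2.18 records start and stop dates and dates of dosage change, so whole calendar days are the natural reading. A start and stop on the same date still divides by zero.

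The error also shrinks quickly, to about 1% at 84 days and 0.6% at 180. The documents give no expected share of very short exposures, so an effect on the arm summary is possible but not shown. This stands too.

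Three stronger readings are tempting and should not be drawn.

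- A reader might infer that early stoppers generally show values above 100% and that control exposure as a whole looks better than it was. Values pass 100% only at or near full dose, and the protocol allows dose adjustments and drug holidays. Cumulative dose is unaffected, and the reported duration errs the other way, one day short.
- A reader might infer that every other SAP duration adds a day. Time from HCC diagnosis to randomization (SAP 6.3) does not.
- A reader might infer that the extra day in the TheraSphere interval conceals breaches of the 28-day spacing. The documents do not support this. Gaps of 26 days or fewer still print below 4 weeks. SAP 8.10.1.3 only summarizes the interval descriptively, SAP 8.2 takes deviations from a separate tracker, and SAP 7.1 promises listings of all case report form data. The variable is not split by lobe either, so it could not test the synopsis wording in any form. Adding a day is also the convention for the other time variables in 6.5.1.1, so this is a matter of consistency with the protocol's wording rather than a plain error.

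**Conclusion.** The sorafenib point holds. The duration in SAP 6.5.1.2 is one day short. Assuming full doses on both end days, dose intensity and relative dose intensity are overstated by d/(d − 1): 16.7% at 7 days, 3.7% at 28 and 1.2% at 84. Both are undefined when first and last dose share a date, and no rule covers that case. With partial doses on the end days the overstatement is smaller.

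The consequence is limited to the descriptive control-arm exposure tables of SAP 8.10.1.2 and is material mainly for exposures of a few weeks or less. No efficacy estimate or test uses these variables.

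The TheraSphere interval is a minor consistency point. It reads 0.14 weeks longer than the day count in which the protocol states its spacing, and no breach of that spacing is hidden by it.

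**What to change.** In SAP 6.5.1.2, set duration of treatment (months) = (date of last dose − date of first dose + 1)/30.4375. This makes the denominator match the per-day benchmark, gives a fully dosed patient 100% at any length of treatment, and removes the division by zero. State also how the calculated administered dose treats the first and last dates, so that numerator and denominator visibly cover the same days.

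In SAP 6.5.1.1, report time between TheraSphere treatments (weeks) = (treatment date − date of previous treatment)/7, or give it in days, so that it reads on the protocol's scale. The protocol's two statements of the spacing, one by lobe and one not, should be reconciled by the sponsor. This note takes no view on which applies.

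The cost is two formula edits and one clarifying sentence. No new data are needed, and no efficacy analysis changes.

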6.5.1.3 Extent of Study Exposure and Follow-up

The duration of survival follow-up and duration of follow-up from last study treatment will be determined.

Duration of survival follow-up (months) = (date of death/last known aliverandomization date + 1) / 30.4375

Duration of follow-up from last study treatment is defined as the time from last study treatment (TheraSphere or sorafenib) until date of death due to any cause or last contact date when patient was known to be alive.

Duration of follow-up (from last study treatment) (months) = (date of death/last known alive – date of last dose of study treatment + 1) / 30.4375

6.5.2 Adverse Events

Treatment Emergent Adverse Events (TEAEs) are AEs which were not present at the initiation of sorafenib or first angiogram or worsened in severity following treatment. If the imputed AE start date starts on or after the first dose of sorafenib or first angiogram and prior to 30 days after last dose of sorafenib or TheraSphere then it is considered a TEAE unless the AE was an ongoing event (end date of one AE matches start date of the next) that started prior to first dose of sorafenib or first angiogram and the grade did not worsen.

The investigator's verbatim term of the AEs will be mapped to system organ classes (SOC) and preferred terms using the MedDRA Version 14.0 dictionary (Medical Dictionary for Regulatory Activities). The investigator will use the NCI Common Toxicity Criteria for Adverse Events [CTCAE] (version 4.0) or the protocol specific criteria when no NCI CTC criteria are available for the adverse event to determine the severity of the AEs.

Adverse events related to sorafenib, device, and angiographic procedures are defined as those events recorded on the eCRF with relationship of possibly, probably, or definitely related.

The incidence of TEAEs will be the number of patients who had the AE (counted only once per patient) divided by the number of patients in the safety population and represented as a percentage. The incidence of AEs will be the number of times an event with the same preferred term occurs, counting worsening events only once. For worsening events, the AE end date of the earlier AE will be the same as the start date of the same AE with a higher severity.

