#### Analysis of secondary efficacy endpoints

Comparison between treatment groups for all secondary endpoints will be conducted at the final analysis with a two-sided alpha of 0.05.

Time to event endpoints (ie, TTP, TTSP, Time to worsening of PVT) will be compared between treatment arms using a log-rank test. Tumor response rates will be compared between treatment arms using the continuity adjusted Newcombe-Wilson test. The

FACT-Hep score will be compared between treatment arms using a mixed linear model with baseline score and the relative time from baseline as covariates.

Safety Analysis: All patients who received study treatments at least once will be included in the safety analysis. All adverse events will be reported according to the National Cancer Institute Common Terminology Criteria for Adverse Events v 4.0 (CTCAE) grades and coded using the Medical Dictionary for Regulatory Activities (MedDRA). The incidence of treatment-emergent adverse events (events which were not present at baseline or worsened in severity following the start of treatment) will be summarized according to MedDRA primary system-organ class (SOC) and preferred term . Laboratory values will be summarized by treatment group over time and overall.

Poolability and Other Analysis: Multivariate Cox regression analysis of time-to-event efficacy endpoints will be conducted on stratification criteria and other factors such as age, gender, duration of disease prior to randomization.

As a sensitivity analysis, to address the poolability of data across regions (ie, Europe, North America, Asia), study sites and gender, a Cox regression analysis of the primary efficacy endpoint, OS, will be conducted with factors of region, study site and gender, and to determine the impact of these factors on OS. Note: region and study site will not be included simultaneously in the model due to collinearity.

Should the impact of region, site or gender on OS be statistically and clinically relevant, the reasons for the observed differential treatment effect, such as patient demographic or clinical characteristics, will be investigated and reported. If the poolability of OS results are in direct question as a result of this sensitivity analysis, the primary endpoint (OS) will also be analyzed separately by region, site or gender.

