### 10.2.4 SAFETY ANALYSIS

The safety analyses will be performed on the SAP population.

All treatment emergent adverse events (TEAEs), (defined as events which were not present at baseline or worsened in severity following the start of treatment) will be reported according to NCI Criteria. The incidence of TEAEs will be summarized according to the MedDRA coded primary system-organ class (SOC) and preferred term. The summaries will be presented overall (severity grades 1-5) and for grade ≥3 events and by treatment discontinuation. These summaries will present the number and percentage of patients reporting an adverse event for each classification level as well as the number of events reported.

Serious adverse events (SAEs) will be tabulated by treatment group.

Laboratory values will be summarized by treatment group over time and overall.

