7.3.1 Partial Date Imputation

Partial dates with day or day and month missing will be imputed as follows:

Missing day only

- The missing day of onset of an AE or start date of a concurrent therapy will conservatively be set as follows:
 - The first day of the AE/concurrent therapy start month, if the month of randomization is before the AE/concurrent therapy start month.,
 - One day after randomization, if the month of randomization is the same as the AE/concurrent therapy start month.
- The missing day of the end date of a concurrent therapy will be set to the last day
 of the month occurrence.
- For other variables, including date of tumor response, progression, death, partial
 dates that need to be imputed will use the 15th of the month to replace the missing
 day. The only exception is when the last visit date is after the 15th of the month
 then death date will use the last visit date on study.

Missing day and month

- If the onset date of an AE or start date of a concurrent therapy is missing both day and month, it will be set as follows:
 - January 1 of the AE/concurrent therapy start year, if the year of randomization is before the AE/concurrent therapy start year,
 - One day after randomization, if the year of randomization is the same as the AE/concurrent therapy start year.

If the resolution date of an AE or end date of a concurrent therapy is missing both day and month, it will be set to December 31 of the AE/concurrent therapy end year.

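### Partial adverse-event onset dates are imputed from randomisation but treatment-emergent status is tested against first treatment, and the SAP's 30-day end limit is not recorded as a change from the protocol (minor)

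*SAP*

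**What the plan says.** **Status test.** SAP 6.5.2 compares the imputed onset date with first sorafenib dose or first angiogram: "If the imputed AE start date starts on or after the first dose of sorafenib or first angiogram and prior to 30 days" after the last dose of either treatment. The opening sentence of 6.5.2 gives a definition with no end; the 30-day limit comes in the operational sentence that follows.

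**Imputation.** SAP 7.3.1 introduces its missing-day rule with "The missing day of onset of an AE or start date of a concurrent therapy will conservatively be set as follows". It then gives two cases: "One day after randomization, if the month of randomization is the same as the AE/concurrent therapy start month", or "The first day of the AE/concurrent therapy start month, if the month of randomization is before the AE/concurrent therapy start month". With day and month both missing, the same-year rule is "One day after randomization, if the year of randomization is the same as the AE/concurrent therapy start year", and a later year takes 1 January. First treatment is not mentioned.

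**Timing.** Sorafenib is to start within two weeks of randomisation (Protocol 9.2.16.2). Angiography is to be done within two weeks (Protocol Synopsis, Treatment Arm Study Treatment).

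**Protocol definition.** Protocol 10.2.4 defines treatment-emergent events as "events which were not present at baseline or worsened in severity following the start of treatment", with no end date; the Synopsis agrees. Protocol 10.2.4 also says "Serious adverse events (SAEs) will be tabulated by treatment group", without a treatment-emergent qualifier. In SAP 8.10.2 the serious-event table by system organ class and preferred term covers treatment-emergent events only.

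**Recorded changes.** SAP Section 5 records the dropped interim analyses and the removal of death from time to progression. It does not mention an end limit for AEs.

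**The concern.** The two SAP sections use different reference dates for one flag. Randomisation comes first and treatment later, so an imputed date set at randomisation plus one day, or at the first of a month, can fall before treatment when the event itself came after. For those events the rule is the opposite of conservative: it removes from the treatment-emergent tables events that belong there. SAP 6.2.1 already sets safety relative day 1 at first dose or first angiogram, so the imputation rule is out of step with the rest of the safety section.

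The end limit raises a different question. TheraSphere is one to three administrations and sorafenib is ongoing, so a window closing 30 days after the last dose can cover quite different lengths of time in the two arms. Percentages from unequal windows will be read side by side. Later serious, fatal or device-related events would be missing from the tables by system organ class and preferred term. Safety is a stated objective and AEs are a listed secondary endpoint.

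**Working it through.** The documents give no figure on this point, so there is none to reproduce. The check applies the SAP's date rules to a calendar.

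**Examples**
- Randomised 3 March, first dose 14 March, true onset 20 March, day missing. Imputed onset is 4 March, before 14 March, so not treatment-emergent.
- Randomised 25 March, angiogram 6 April, true onset 15 April, day missing. Imputed onset is 1 April, before 6 April, so not treatment-emergent.

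**Day missing: share dated before treatment**

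Assumptions: randomisation on each of 365 days, lag to first treatment equally likely on 0–14 days (or 2–14 days), true onset uniform over the stated period.

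- With a lag of 0 or 1 day nothing is lost.
- With a lag of 2 days or more, every event in the remainder of the calendar month of first treatment is lost, unless treatment starts on the 1st.
- Mean days left in the month, counting the treatment day: (7 × 496 + 4 × 465 + 1 × 406)/365 = 5738/365 = 15.72. Here 496, 465 and 406 are the sums 1 to 31, 1 to 30 and 1 to 28.
- Treatment starts on the 1st take out 365/365 = 1.00 day, leaving 14.72 days lost on average.
- For lags of 0–14 days, multiply by 13/15.

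| True onset within | Lag 2–14 days | Lag 0–14 days |
|---|---|---|
| 30 days | 14.72/30 = 49.1% | 42.5% |
| 60 days | 14.72/60 = 24.5% | 21.3% |
| 90 days | 14.72/90 = 16.4% | 14.2% |

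Full enumeration gives the same figures. If imputation is anchored on first treatment, the share is 0% throughout.

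**Only the year known (by enumeration):** 83–96% within 30 days and 76–88% within 90 days are dated before treatment.

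**Net effect in the 30-day tables**

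The first-of-month rule also pulls events that start just after the window closes back into it. The mean gain is again 14.72 days. At a constant event rate:

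| Window | Lost | Gained |
|---|---|---|
| 44 days | 29.0–33.5% | 14.72/44 = 33.5% |
| 197 days | 6.5–7.5% | 14.72/197 = 7.5% |

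Losses and gains nearly cancel. With no end limit nothing is gained, and over 274 days (the planned 9-month control median) 4.7–5.4% is lost.

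**Window length, from first treatment to 30 days after the last dose**
- One TheraSphere infusion, angiogram in Week 2 and infusion in Week 4: 14 + 30 = 44 days.
- Three infusions at the minimum 28-day spacing: 14 + 28 + 28 + 30 = 100 days.
- Re-treatment at an assumed 5.5 or 7.9 months: 14 + 5.5 × 30.4375 + 30 = 211 days, or 14 + 7.9 × 30.4375 + 30 = 284 days.
- Sorafenib for an assumed 1, 2.8 or 5.5 months: 60, 115 or 197 days. The documents give no sorafenib duration; 2.8 and 5.5 are time-to-progression medians quoted in the protocol background.

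Against a single infusion the sorafenib window is 60/44 = 1.4 to 197/44 = 4.5 times as long. With re-treatment the order can reverse.

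**The case against.** **Few events are affected.** Protocol 12.3 requires an onset date for every AE, visits are frequent, and records are monitored against source. The percentages are shares of the exceptions, not of all treatment-emergent events. This stands and limits the size of the point.

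**No bias is shown.** A reader might infer that the rule undercounts treatment-emergent events, or favours one arm. The working does not support that for the 30-day tables: losses and gains nearly cancel, and the windows can differ in either direction. What remains is that the wrong events are counted: some close to treatment go out and some late ones come in.

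**The 30-day limit is a legitimate choice.** Such limits are a normal convention, and SAP 6.5.3 uses 30 days for laboratory data. The operational sentence in 6.5.2 does not say "only if", though a limit is its likely reading. So the choice is not an error. It does narrow the protocol's definition without being recorded as a change.

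**Safeguards exist.** SAP 8.10.2 lists all AEs, serious events and fatal events by patient, makes no statistical comparison, and has overall-summary rows for serious and device events without a treatment-emergent qualifier. Deaths count in overall survival. The trial ended early with limited numbers, so listings can be read directly. All of this stands.

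**Months before randomisation.** A reader might also object that 7.3.1 has no rule for a missing day in a month before randomisation, although AEs are collected from consent. Such an onset precedes treatment whatever day is chosen, so treatment-emergent status cannot change.

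**Conclusion.** The concern holds as a minor point in two parts.

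First, the imputation rule is wrong for its purpose. As written, it classes some events that start after treatment as not treatment-emergent: about 43–49%, 21–25% and 14–16% of day-missing events with true onset within 30, 60 and 90 days. These figures assume randomisation spread evenly over the year and treatment within the protocol's two weeks. The count of partial-date events is not given and is probably small.

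Second, the 30-day end limit departs from the protocol's definition and is not recorded in SAP Section 5. The resulting windows can differ by arm, but the direction depends on sorafenib duration and TheraSphere re-treatment, which the documents do not fix.

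The documents do not support a claim that the safety comparison is biased towards either arm, or that the 30-day convention is itself improper.

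**What to change.** **(a) SAP 7.3.1.** When the known month (or the year, if the month is missing) contains the date of first sorafenib dose or first angiogram, and neither the event's end date nor other recorded information shows earlier onset, impute that date. Otherwise use the first day of the known month or year. Report the number of imputed onsets by arm.

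**(b) SAP Section 5 and 8.10.2.** Record the 30-day limit as a change from the protocol. Keep the 30-day tables, and add supplementary tables of AEs, serious events, device effects and fatal events under the protocol's definition, with no end limit.

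**Cost.** SAP wording, one reprogrammed flag and a few repeated tables; no new data are needed.

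**Downsides to state in the SAP**
- (a) moves some true pre-treatment day-missing events into the treatment-emergent set. With onset uniform from 14 days before randomisation to the day before treatment, the share is up to about 62% if no end date rules them out, and about 9%, 25% or 48% if end dates are recorded and events last an assumed 3, 7 or 14 days. It is 0–7% now.
- In the 30-day tables, (a) alone removes the early loss but not the late gain (about a third in a 44-day window, 7.5% in a 197-day window). That leaves an over-count that differs with window length, so (a) and (b) belong together.
- (b) brings in late disease-related events and toxicity of post-progression therapy over unequal follow-up. Protocol 9.2.16.3 allows sorafenib as best available care, so the TheraSphere-arm tables could absorb its toxicity. For that reason these tables are supplementary.
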